## 6.3 Subject Elimination Criteria

- (1) The subjects seriously violate the inclusion/exclusion criteria, affecting the evaluation of the primary endpoint.
- (2) The subjects do not use the test devices for treatment after inclusion, or have no any visit record although they meet the inclusion criteria.

## 6.4 Statistical Methods

### 6.4.1 Statistical Design

This study is a prospective, multicenter and randomized controlled design, with comparison type of non-inferiority test. It is to demonstrate that the investigational medical device also meets the needs of clinical application through comparison with the similar products that have been marketed, with the primary endpoint set as device success rate (lesion level); the corresponding statistical hypothesis test is:

$$H_0 : p_T - p_C \leq -\Delta$$

$$H_1 : p_T - p_C > -\Delta$$

Where,  $p_T$  is the expected device success rate in the test group,  $p_C$  is the expected device success rate in the control group, and  $\Delta$  is the non-inferiority margin.

## 6.4.2 Statistical Analysis Methods

### (1) General Principles for Statistical Analysis

In this study, SAS software is used for data description and analysis. All statistical tests are conducted by two-sided test (unless otherwise specified). The 95% confidence is adopted for the confidence interval (CI). In addition to the statistical methods listed below, detailed and additional exploratory analyses may be required and confirmed in the Study Reports and Statistical Analysis Plan (SAP).

- 1) Statistical description: For the description of quantitative indicators, the mean, standard deviation (SD), median, minimum, maximum, lower quartile (Q1) and upper quartile (Q3) will be calculated; for the categorical indicators, the number of cases and percentage for each category will be described.
- 2) Statistical inference: The inter-group comparison in general condition will be conducted by using appropriate method according to the types of indicators. The inter-group comparison in quantitative data will be conducted by the group t-test (homogeneity of variance and normal distribution) or Wilcoxon rank sum test according to the data distribution. The categorical data will be analyzed by the Chi-squared Test or Exact Test (if the Chi-squared Test is not applicable), while the ranked data will be analyzed by the Wilcoxon rank sum test or CMH test.

### (2) Completion and Baseline Analysis

The number of subjects enrolled and the completion status of enrollment of each site should be summarized, and the drop-out cases should be listed. Different data set sizes in each group, case distribution of each site, total drop-out rate comparison and reasons for discontinuation, should be tabulated in detail. The demographic characteristics (age and gender), the relevant medical history and the treatment history of the patients are described, and the comparison of age and gender, etc. between the two groups will be conducted to measure the comparability between the two groups. Demographic analysis is based on FAS.

### (3) Primary efficacy endpoint

The Primary efficacy endpoint of this study is the device success rate (lesion level), and the hypothesis test is as follows:

Null hypothesis:  $P_T - P_C \leq -10\%$

Alternative hypothesis:  $P_T - P_C > -10\%$

Under  $\alpha=0.025$  (one-sided test) and  $\beta=0.2$ , the device success rate (lesion level) is compared between the test group and control group, and the difference between the two groups and the 95%CI of such difference are calculated to determine whether the non-inferiority margin is met based on the lower limit of CI. Non-inferiority is established if the lower limit of 95%CI is not lower than -10%. If

central effect is to be considered, CMH's chi-square test is used.

#### **(4) Secondary efficacy endpoints**

The secondary efficacy evaluation is based on FAS and PPS. For the statistical description and inference of the data, the applicable descriptive indicators and hypothesis test methods are selected based on the characteristics of the data.

#### **(5) Safety endpoints**

Descriptive analysis is performed on safety endpoints data, and the number, incidence and case-times of all AEs, related AEs and SAEs in the two groups are calculated. The cases who discontinue the study due to AEs and who experience SAEs are presented in a list.

### **6.4.3 Significance Level and Power of Clinical Study**

In this trial, for the primary endpoint, the significance level of statistical test is 0.025% one-sided, and the power of test is taken as 80%. For other indicators, the significance level of statistical test is taken as 0.05 two-sided.

### **6.4.4 Expected Drop-out Rate**

In determining the sample size, the highest possible drop-out rate during the study is expected to be 10%, including all conditions that make the subjects ultimately excluded from the primary analysis, often referring to major deviation of trial protocol (affecting the primary efficacy evaluation and/or safety evaluation) adjudicated by the PIs.

### **6.4.5 Pass/Fail Criteria for Clinical Trial Results**

Determining whether the study result is acceptable from a statistical perspective is equivalent to verifying the initial hypothesis testing. For this study, the primary evaluation indicator is the device success rate (lesion level). In comparison type, this is non-inferiority test. It is planned to prove through the study results that the test group had the same therapeutic effect as compared with the control group.

In conclusion, the judgment of the study results will be based on the difference in device success rate between the test group and control group. If the results show that the lower limit of 95%CI for the difference in device success rate between test group and control group is greater than -10% (the pre-specified non-inferiority margin), the non-inferiority is established. Otherwise, the non-inferiority conclusion is not established.

### **6.4.6 Criteria for Termination of Trial Based on Statistics and Justification**

The interim analysis and its corresponding early termination criteria are not pre-established in this trial, so this section is not applicable. All statistical analyses are conducted after the completion of data collection, cleansing and final locking.

### **6.4.7 Procedures for Reporting Deviation from Original Statistical Plan**

The statistical analysis plan needs to be confirmed by the sponsor and the PIs, and finalized before database locking. Prior to finalization, the initial analysis plan should be modified according to the actual conditions in the trial process. In principle, the main analysis principles, methods and analysis sets should not be modified, and all the modifications will be recorded.

## 6.5 Missing Data and Outliers

Method for the treatment of missing data: The missing data will be processed according to the division of the data set; primary efficacy data will be imputed with the use of the WOCF (Worst Observation Carry Forward).

Wrong data handling method: In the process of data management, the quality management will be performed for the data in the database, wrong data found will be questioned in the form of Query to investigators, and the wrong data will be adjusted according to the written reply of investigators until all wrong data is corrected before locking the database.

Unreasonable data handling method: In the process of data management, the data in the database will be checked logically, unreasonable data found will be questioned in the form of Query to investigators, and the unreasonable data will be adjusted according to the written reply of investigators until all unreasonable data is solved before locking the database.

## 7. Monitoring Plan

The sponsor should assume the responsibility for the monitoring of the medical device clinical trial, establish the SOPs for monitoring and choose qualified CRA to perform the monitoring duties. The monitoring plan is as follows:

- (1) Monitoring visits include: before start-up visit, start-up visit, routine process visit, unconventional visit, and closing visit;
- (2) Monitoring frequency: The number of CRAs and the monitoring frequency should depend on the complexity of the medical device clinical trial and the number of study sites involved in the trial.
- (3) CRA qualification: The CRA should be trained accordingly, be familiar with the GCP and relevant laws and regulations, have relevant professional knowledge, be familiar with relevant study data of the investigational medical device, clinical information of the similar products, clinical trial protocol and related documents, and be able to effectively fulfill the monitoring duties; the CRA should abide by the SOPs for monitoring developed by the sponsor, and urge the medical device clinical trial to be carried out according to the clinical trial protocol.
- (4) Monitoring contents: compliance of medical device study sites and investigators with the clinical trial protocol, the GCP and relevant laws and

regulations in the implementation of clinical study; signing of ICF by subjects, screening of subjects, follow-up, rights and interests, and safety guarantee; the management and use of investigational medical devices and control devices (if applicable); the management and use of biological samples (if applicable); handling of adverse events and device defects; reporting of safety information; recording of clinical trial data and filling of CRFs.

## **8. Data Management**

The Electronic Data Capture (EDC) system is used to collect the trial data. The EDC system has been strictly tested and fully complies with the requirements of Good Clinical Practice for Medical Devices and Technical Guidance for Data Management in Clinical Trials. Before the system is formally launched, the relevant users need to be trained and assessed to ensure that the system meets the trial requirements. After the official launch, relevant personnel will be provided with the account and password. The account is bound with the role and authority of the user who is required to properly keep and not to disclose the account information to others or exercise corresponding rights on behalf of others.

### **8.1 Data Collection**

The EDC directly transmits data from the client to the server through the Internet. Investigators can directly enter the source data into the EDC system to complete data collection. Investigators should be responsible for the quality of the entered data and ensure the authenticity and integrity of the data. The EDC system provides an interface printing function that allows the investigators to print the electronic case report form (eCRF) as required.

### **8.2 Data Verification and Modification**

The EDC system provides on-line and off-line verification methods. When investigators have entered abnormal data, the EDC system will issue real-time warnings to remind them to check; and the data administrator performs logical check on the data stored in the server and issues the wrong data through EDC in the form of manual query. Investigators need to answer all published queries. The CRA needs to periodically remind and assist the investigators in answering queries to ensure that each query is handled correctly. The system will record all queries and answers thereto.

### **8.3 Database Locking**

When all data entry is completed and submitted, and all queries are answered, the system enters a soft locking status. The data administrator will generate a blinded review report based on the database. If it is confirmed that the data would not be modified, the sponsor, the person in charge of data administration and the person in charge of statistics will sign the database locking form, and the data administrator would complete the database locking operation according to the

form. The locked database cannot be modified again. If there is any wrong data that affects the primary efficacy endpoint or safety endpoints, the sponsor, the person in charge of data administration and the person in charge of statistics will confirm the unlocking for modification and sign the database unlocking form, and the data administrator will modify the wrong data according to the unlocking reason and carry out quality control. The sponsor, the person in charge of data administration and the person in charge of statistics will sign the database locking form again once the error has been corrected.

## **9. Risk-Benefit Analysis**

### **9.1 Benefit Analysis**

PTCA, as the most basic method in the PCI of coronary artery stenosis lesions, has been widely used in patients with coronary artery in situ lesions or ISR. Based on data of its previous clinical applications, PTCA shows potential benefits in improving patients' symptoms and quality of life that outweigh possible risks associated with the use of such products. This also benefits from the design of the scoring balloon itself, with three wound Ni-Ti alloy elements to the outside of the common balloon. Therefore, compared with the risks such as late stent delivery failure and stent incomplete expansion caused by the blunt, disorderly dilated lesion with the common balloon, the scoring balloon dilates lesions in such a way that plaque cracks can be formed in an effective and relatively regular manner, thus obtaining ideal stent implantation, effectively reducing the restenosis and the risk of in-stent thrombosis, and ultimately affecting the whole procedure time and procedural success rate [18-20].

In addition, there is also a possibility that subjects do not directly benefit from enrollment in this trial, but the results of the trial will also help to improve existing treatment methods and benefit the patients with coronary artery stenosis requiring balloon dilation in the future.

### **9.2 Potential Risk Analysis**

There may be some risks involved in participating in this trial, but the risks are not expected to be substantially different from those experienced by individuals receiving balloon dilation or PCI outside of the trial. Patient risks are managed and reduced by fully evaluating the potential risks and benefits of subjects, providing comprehensive trainings to the investigators, and conducting regular monitoring visits during the clinical trial process, and adhering to the recommended peri-procedural medication regimen.

## **10. Quality Control of Clinical Trial**

### **(1) Quality Control Measures of the Laboratory**

The laboratories of the participating clinical trial institutions should have quality

control procedures for all observed indicators of this trial.

## **(2) Training for Clinical Trial**

Before the initiation of the clinical trial, the relevant personnel of the clinical trial will be trained, and the investigators of each site will be trained by organizing the kick-off meeting, including the clinical protocol, informed process, device use, and document filling, etc. In the course of the trial, targeted training will be provided to the investigators and the relevant personnel of the trial according to the actual clinical situation.

## **(3) Monitoring of Clinical Trial**

During the clinical trial, the CRA will conduct regular monitoring visits at the study site according to the monitoring plan, to ensure that all the contents in the study protocol are strictly observed, and will check the raw data to ensure that the filled contents of EDC are true, complete and correct.

## **(4) Retention of Raw Data**

The raw data of this trial include the signed ICF, release records of test products, relevant laboratory test reports, case records and other related records, which should be retained at the clinical trial institute of the hospital where the study site is located. All raw data and printed CRF should be retained for 10 years after completion or termination of the clinical trial.

# **11. Ethical Issues and Informed Consent in Clinical Trial**

## **11.1 Ethical Considerations**

This clinical trial is conducted in compliance with the Declaration of Helsinki of the World Medical Association and applicable laws and regulations of China. Before the clinical trial, the investigators need to submit the clinical trial protocol, ICF and other related documents to the Medical Ethics Committee of hospitals where the study sites are located. The clinical trial will be started only after obtaining the approval of the EC. Any amendment to the study protocol must be approved by the EC before it can be implemented. SAEs during the clinical trial shall be submitted to the EC in writing timely.

## **11.2 Informed Consent Process**

The investigators should comply with the codes of ethics and relevant ethical requirements of the Declaration of Helsinki of the World Medical Association. Before subjects participate in the clinical trial, the investigators should inform the subjects of the details of the investigational medical device and clinical trial, as well as the possible benefits and known and foreseeable risks. After full and detailed explanation by the investigators, both the subjects and investigators should sign and date the ICF; where a subject is a person without or with limited capacity for civil conduct, the written informed consent should be obtained from

his/her guardian; if any subject lacks reading ability, an impartial witness should be present to witness the whole informed consent process, and sign and date the ICF. The investigators should not compel or otherwise improperly induce the subjects to participate in the clinical trial;

The investigators should use the latest version of the ICF approved by the EC and other information provided to subjects. Where the ICF is revised in the course of the trial, the revised ICF should not be implemented until the written consent of the EC has been obtained again. When the ICF is updated and reviewed and approved by the EC, the investigators should ensure that all the subjects who have been affected and have not finished the trial procedures sign the newly revised ICF.

## **12. Provisions for AE and Device Defect Reporting**

### **12.1 Definition of AE and Provisions for AE Reporting**

Adverse event (AE) refers to an adverse medical event that occurs during the medical device clinical trial, related or unrelated to the investigational medical device.

AEs after treatment with the investigational product must be recorded truthfully in the Adverse Event Form. Record the duration of AEs (that is, from start to end), severity, and correlation with the clinical study as well as the corresponding treatment and other management measures. Follow-up shall be made to the end of the trial or the outcome of adverse events.

In this clinical trial, the following conditions may not be recorded as an AE: 1) hematoma less than 6 cm or a small amount of bleeding at the puncture site; 2) common stress reactions post-procedure, such as fever and weak dorsalis pedis artery pulse; 3) abnormal laboratory indicators post-procedure are clinically significant, but the investigators do not take corresponding treatment measures, and the subjects resolve spontaneously.

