#### **5. Study Design**

##### **5.1 Overall Design and Its Determination Basis**

This clinical trial is a prospective, multicenter, randomized, parallel controlled, non-inferiority design.

Multicenter clinical trial: refers to the clinical study conducted in two (inclusive) or more medical device clinical trial institutions under the same clinical trial protocol.

Parallel controlled design: Based on the Guidance for the Design of Medical Device Clinical Trials, the controlled clinical trial is conducted using the marketed devices with recognized efficacy/safety. The Coronary Scoring Balloon Catheter is a class III medical device, and there are few similar products on the market. In order to evaluate the effectiveness and safety of Coronary Scoring Balloon Catheter, the NSE Coronary Dilatation Catheter (NMPA (I) 20163035067), which is similar in structure and operating principle, relatively widely used in clinical practice and has positive efficacy in China and abroad, is

selected as the control device after investigation.

**Randomization:** Randomization is the basic principle to be followed by parallel controlled clinical trials. Each subject in a clinical trial has the same opportunity (the ratio of cases in test group to control group is 1:1) to be assigned to test group or control group, without affection of subjective wishes of the investigator and/or subject, to ensure the subjects in test group and control group comparable in various known and unknown baseline variables that may affect the trial result.

**Blinding:** Due to the different inherent characteristics (appearance, marking, etc.) of the investigational medical device and the control device, the subjects and investigators cannot be blinded in the trial, so an open-label design is adopted.

**Non-inferiority test:** The non-inferiority test is selected to confirm the efficacy/safety of the investigational medical device, which if lower than that of the control device but the difference between them is less than the pre-set non-inferiority margin, the difference is clinically acceptable.

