## **(3) Follow-up period (from post-procedure to pre-discharge)**

- 1) Vital signs (systolic blood pressure, diastolic blood pressure and heart rate);
- 2) Post-procedure reexamination of blood routine and blood biochemistry: ① Blood routine: white blood cell count (WBC), red blood cell count (RBC), platelet count (PLT) and hemoglobin (HB); ② Renal function: serum creatinine (SCr); ③ Liver function: alanine aminotransferase (ALT) and aspartate aminotransferase (AST); ④ Blood lipids: triglyceride (TG), total cholesterol (TC), high density lipoprotein cholesterol (HDL-C) and low density lipoprotein cholesterol (LDL-C);
- 3) Myocardial enzyme test 48 hours post-procedure. If the results are abnormal and clinically significant, re-examination should be performed before

discharge (the highest test value is recorded for those with multiple examinations);

- 4) 12-lead ECG examination 48 hours post-procedure.
- 5) AEs (such as procedure-related complications, including puncture hematoma, vascular dissection, vessel perforation, acute occlusion, etc.);
- 6) Cardiovascular adverse events (including major adverse cardiac events - MACE, target lesion failure - TLF, patient-oriented composite endpoint - PoCE);
- 7) Cardiovascular concomitant medications (anticoagulants, antiplatelets, and statins).

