### 12.3 Definition of SAE

The SAE refers to the event that causes death or serious deterioration of health in the process of clinical trial, including:

- (1) Fatal disease or injury;
- (2) Permanent impairment of a body structure or a body function;
- (3) Requiring in-patient hospitalization or prolongation of existing hospitalization;
- (4) Requiring medical measures to prevent permanent impairment of the body structure or body function;
- (5) Leading to fetal distress, fetal death or congenital abnormality, or congenital defect, etc.

Hospitalization or prolongation of hospitalization cannot be considered an SAE if at least one of the following exceptions is met:

- Pre-planned hospitalizations (e.g., scheduled elective or scheduled operations or examinations prior to study start)
- Hospitalization not related to an AE (e.g., community hospitalization for short-term or long-term care purposes)

However, any interventional therapy performed during hospitalization may meet the criteria for an "Important Medical Event" and may be reported as a SAE based on clinical judgment. In addition, if local regulatory authorities specifically require stricter definitions, local regulations shall prevail.

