2.2. Safety Evaluation

1) Target lesion failure composite endpoint (TLF) incidence

Any of the following events constituted a TLF:

- a. Cardiovascular death (including cases where the cause of death is uncertain but considered cardiovascular in origin);
- b. Target Vessel-Related Myocardial Infarction (TV-MI);
- c. Clinically-indicated target lesion revascularisation (CI-TLR).

Evaluation method: The observation period spans from the commencement of procedure until discharge. For each subject, the incidence rates of individual events and the composite event rate are calculated.

2) Incidence of the patient-oriented composite endpoint (PoCE)

Any occurrence of the following events constituted a PoCE:

- a. All-cause mortality;
- b. All myocardial infarctions;
- c. All recurrent revascularisation events, including target lesion revascularisation (TLR), target vessel non-target lesion revascularisation (TVR), and non-target vessel revascularisation.

Evaluation method: The observation period spans from the commencement of procedure until discharge. For each subject, the incidence rate of individual events and the composite event rate shall be separately calculated.

3) Incidence of Individual Adverse Events and Serious Adverse Events

Evaluation Method: The observation period spans from the commencement of procedure until discharge. Other potential adverse events include balloon rupture, vascular perforation, dissection, acute occlusion, vasospasm, thrombosis (including in-stent thrombosis), and arrhythmias requiring intervention. The incidence rate of each individual event shall be separately calculated.

4) Incidence of device deficiency

3. Analysis Data Set

Full Analysis Set (FAS): The population defined according to the intention-to-treat principle, comprising all subjects who were randomised and received the study product. For patients with missing primary efficacy endpoint data, worst observation carried forward (WOCF) was applied.

Per-protocol set (PPS): Subgroup of the completed trial population excluding major protocol deviations (e.g., subjects breaching inclusion or exclusion criteria).

Safety Set (SS): Refers to the dataset comprising subjects who used the investigational device and for whom safety endpoints were recorded.

Efficacy analyses will be conducted based on both the full analysis set and the per-protocol set. All baseline demographic analyses utilise data from the full analysis set, while safety evaluations employ the safety set.

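### Protocol 12.1 lets an unblinded decision not to treat keep a clinically significant laboratory abnormality out of the AE counts, gives its exemptions no override for serious events, and conflicts with 5.5.2 on puncture haematoma.

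*Protocol*

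**What the plan says.** Protocol 12.1 counts as an AE any adverse medical event during the trial, whether or not the device caused it, and requires AEs after treatment to be recorded. It then makes an exception: "In this clinical trial, the following conditions may not be recorded as an AE". Three groups follow:

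- Exemption 1: "hematoma less than 6 cm or a small amount of bleeding at the puncture site".
- Exemption 2: "common stress reactions post-procedure, such as fever and weak dorsalis pedis artery pulse".
- Exemption 3: cases where "abnormal laboratory indicators post-procedure are clinically significant, but the investigators do not take corresponding treatment measures, and the subjects resolve spontaneously".

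The other relevant places are:

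- Protocol 5.1: "the subjects and investigators cannot be blinded in the trial".
- Protocol 5.5.2, under both the procedure and the follow-up period, lists among the items to collect "AEs (such as procedure-related complications, including puncture hematoma, vascular dissection, vessel perforation, acute occlusion, etc", with no size limit for the haematoma.
- Protocol 12.3 includes among the SAE criteria "Requiring in-patient hospitalization or prolongation of existing hospitalization". It also says that a stay, or a longer stay, is not an SAE when it is unrelated to an AE, and gives community care as the example.
- Protocol 12.4 sets a 24-hour reporting duty that runs from the investigator's awareness of an SAE.
- SAP 2.2 makes the incidence of individual AEs and SAEs a safety endpoint. SAP 5.5 compares these rates between groups, and Tables 31 to 34 have a P-value column.
- SAP 5.5 also asks for before-and-after cross-tabulations of laboratory results and a list of the clinically significant ones (Tables 35 to 49).

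**The concern.** Exemption 3 starts from results that the investigator has already judged clinically significant. Two further facts remove them from the AE record: no treatment was given, and they resolved. The first is a decision by someone who knows which balloon was used. If the tendency to treat differs by arm, the recorded AE rates differ even when the true rates are equal. If it does not differ, the AE rate is still understated in both arms.

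Two wording problems add to this. Section 12.1 does not say what happens when an exempted condition also meets a seriousness criterion. And a site following 12.1 would omit a small puncture haematoma that a site following 5.5.2 would record. The phrase that introduces the list can be read as permission or as prohibition, so sites may also differ in how they apply all three exemptions.

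**Working it through.** **Who decides under exemption 3.** The exemption needs three things together: a laboratory abnormality judged clinically significant, no corresponding treatment, and spontaneous resolution. The first two are the investigator's decisions, and 5.1 says the investigator is not blinded. The treatment decision is therefore part of the rule for counting an AE.

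**Where an exempted result still appears.** It appears in Tables 35 to 49, which are laid out by arm and do not depend on treatment, and in the listing of clinically significant abnormalities. It does not appear in Tables 31 and 32, which give AE incidence, severity, relatedness and coded terms. Tables 35 to 49 have no column for severity, relatedness or a between-arm statistic, so they reduce the loss but do not replace the AE tables.

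**The SAE route.** Section 12.3 defines an SAE as an event, not as a recorded AE, and 12.4 does not make reporting depend on an AE form entry. On those two texts, an exempted condition that prolongs the stay remains an SAE. The opening lies in 12.3's own exception for a stay unrelated to an AE. If 12.1 is read as saying that the condition is not an AE, someone could argue that the longer stay falls under that exception. No sentence in 12.1 closes this off.

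**Haematoma.** Section 12.1 exempts puncture-site haematomas under 6 cm. Section 5.5.2 names puncture haematoma as an example of an AE to collect, at any size. SAP Table 30 has a puncture-site row (its English label reads oedema, not haematoma) and does not say which rule feeds it.

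**Size.** The denominator is the planned arm size in Protocol 6.1.1, which reproduces: 7.85 × (2 × 0.96 × 0.04) / 0.10² = 60.29, rounded up to 61; 61 / 0.9 = 67.8, rounded up to 68. One subject whose only event is exempted moves an arm's AE incidence by 1/68 = 1.47, or about 1.5 percentage points.

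For any bias between arms, let p be the true proportion of subjects with a clinically significant abnormality that resolves, equal in both arms, and let u be the share left untreated in an arm. The recorded rate in that arm is p × (1 − u), so the spurious difference is p × |u_T − u_C|. The documents give neither p nor u. The values below are assumptions that show the range only:

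| p | u equal in both arms | u differs by 10 points | u = 80% v 50% |
|---|---|---|---|
| 5% | 0 | 0.5 points | 1.5 points |
| 10% | 0 | 1.0 points | 3.0 points |
| 20% | 0 | 2.0 points | 6.0 points |

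For the row p = 10% with 80% v 50%: 6.8 subjects × 0.2 = 1.36 recorded and 6.8 × 0.5 = 3.4 recorded; the difference is 2.04 / 68 = 3.0 points. If u is equal and the true rates differ, the recorded difference is the true one multiplied by (1 − u).

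**The case against.** The case for leaving the text alone has real force.

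- **SAE reporting.** A reader might infer that exempted events never reach the 24-hour route, so that SAEs go unreported. The documents do not support that. Section 12.1 says nothing about hospital stay, 12.3 and 12.4 stand without an AE form entry, and the example given for the 12.3 exception is community care. What stands is narrower: the texts leave room for an argument that one sentence would end.
- **Resolution.** Follow-up ends at discharge, and a repeat test is required only for abnormal, clinically significant myocardial enzymes. A reader might infer that unresolved abnormalities also escape. They do not, because exemption 3 requires resolution. If it has not been seen, the exemption is not met and the event is recordable.
- **Loss of data.** A reader might infer that these results disappear from the safety report. They do not: the laboratory tables and listing show them by arm, and a troponin rise that meets the infarction definition in Protocol Appendix 5 enters the composite endpoints. The loss is from the AE counts.
- **Discretion.** The 6 cm limit is a measurement, not an open-label choice. Exemption 2 is confined to common post-procedure reactions. Some judgement remains in what counts as common and as a small amount of bleeding.
- **Haematoma.** Section 5.5.2 gives examples, and 12.1 could be read as setting the threshold for them. That reading is possible, but neither section refers to the other and Table 30 does not settle it.
- **Weight.** Protocol 6.4.2 (5) describes the safety analysis as descriptive, 5.3.2 names TLF and PoCE as the primary safety endpoints, and AE counts play no part in the non-inferiority decision. This limits the importance of the point. However, the SAP does plan between-arm comparisons of AE rates.

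**Conclusion.** The concern holds in a limited form. As written, 12.1 makes the AE count depend partly on an unblinded treatment decision for laboratory results already judged clinically significant. It is silent on how its exemptions relate to 12.3, and it disagrees with 5.5.2 on puncture haematoma.

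The amount of bias is unknown. The unit is 1.5 points per subject, on the planned 68 per arm and for a subject with no other AE. A spurious difference needs unequal non-treatment between arms; at equal shares it is zero. The table above rests on assumed rates and is not an estimate. The primary endpoint and the sample size are unaffected. The point should be corrected because AE incidence is a stated safety endpoint and the correction is small.

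**What to change.** - In Protocol 12.1, delete exemption 3, so that a post-procedure laboratory abnormality judged clinically significant is recorded as an AE whether or not it is treated.
- Add one sentence to 12.1: no exemption applies to an event that meets the SAE definition in 12.3.
- Reconcile 12.1, 5.5.2 and SAP Table 30 on which puncture-site haematomas are recorded, and state in a note to Table 30 which rule feeds its puncture-site row.

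The cost is one protocol paragraph, a matching line in 5.5.2 and a table note, with a haematoma-size field in the EDC if the agreed rule needs one. The downside is more minor AE records and a somewhat higher reported AE rate in both arms.
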